5.3. Multicenter Studies

This is a multi-center trial and subjects were randomized by region (US/Canada vs Central America/South America/Mexico vs Europe/Australia/Israel vs Asia) –see [Appendix 1](#) for details of countries and regions. There will be no summaries performed at the center level.

Enrollment by site will not be presented for the Years 2 to 5 post-treatment follow-up period, as this data has been summarized as part of the Week 52 double-blind treatment period part of the study.

5.4. Examination of Covariates, Other Strata and Subgroups

5.4.1. Covariates and Other Strata

Details of randomization strata are included in the separate Week 52 double-blind treatment period RAP (Section 8.2). Covariates are not relevant for these safety analyses.

5.4.2. Examination of Subgroups

Data from the Years 2 to 5 post-treatment follow-up period will not be summarized by subgroups.

5.5. Multiple Comparisons and Multiplicity

There is no statistical hypothesis to be tested (no formal statistical testing) for the safety analyses, and therefore no need to control for multiple comparisons.

5.6. Other Considerations for Data Analyses and Data Handling Conventions

- All data summaries and analyses will be performed using the latest available version of SAS software (as available at GSK).
- Data displays will follow the shells outlined in the Mock TLFs document which will follow the Benlysta program standards and, as far as possible, follow the agreements proposed by the GSK Integrated Data Standards Library (IDSL).
- The most current version of Medical Dictionary for Regulatory Activities (MedDRA) at the time of DBF will be used for reporting.
- The most current version of the Benlysta PSAP at the time of DBF will be used for reporting.
- Where SDTM terminology differs from the eCRF and/or mock shells, the SDTM terminology will be presented in displays unless otherwise specified.

Unless otherwise stated, the following will apply:

- Continuous variables will be summarized with the statistics mean, median, standard deviation (SD), 25th and 75th percentiles, minimum and maximum.
- Categorical variables will be summarized with frequency counts and percentages, or proportions where specified. A 'Missing' category will be added to frequency counts if there is at least one missing record.
- Percentages will be calculated using the number of subjects in the relevant population/treatment group (denoted by N) as the denominator, unless otherwise stated.
- The minimum and maximum will be reported to the same number of decimal places as the raw data recorded in the database.
- The mean, median, 25th percentile and 75th percentile will be reported to one more decimal place than the raw data recorded in the database.
- The SD will be reported to two more decimal places than the raw data recorded in the database.
- A maximum of four decimal places will be used.
- Percentages will be presented to one decimal place unless otherwise specified (i.e. deaths and malignancies will be presented to 2 decimal places). Incidence rates will be presented to two decimal places.
- A count of zero will have no corresponding percentage.
- Listings will be based on the As-Treated population (unless otherwise specified) and generally be limited to those required by ICH guidelines and will be sorted by treatment group, investigator number, subject number and visit (where appropriate).

MedDRA Coding of Death and Malignancy:

Deaths reported during the Week 52 double-blind study period were collected as adverse event data. In the year 2-5 follow up period for BEL115467 the primary reason of death is collected on the annual FU survival form and will be coded using

the latest version of MedDRA (with SOC and PT); detailed SAE information is NOT collected. There are coding limitations for death data from the post-treatment follow-up period, as the information available to code was limited to the verbatim 'primary reason for death'.

Malignancies reported during the 52-week double-blind treatment period of the study were collected as adverse event data. New primary malignancies reported in the post-treatment follow-up period are collected on the annual FU survival form and will be coded using the latest version of MedDRA (with SOC and PT). There are coding limitations for malignancy data from the post-treatment follow-up period, as the information available to code was limited to the verbatim 'diagnosis'.

For the interim reporting efforts (Years 2, 3 and 4) every effort will be made to code all reported terms, however this may not be possible and there may be un-coded terms for interim reporting efforts.

Data for deaths and malignancies from the Week 52 double-blind treatment period adverse event data will not be re-coded as part of Years 2-5 reporting. Summary tables presenting deaths and malignancies by MedDRA SOC/PT will not include data from the Week 52 double-blind treatment period. Summaries of these data can be found in the Week 52 double blind treatment period CSR and will not be duplicated in the post-treatment follow-up summaries.

A decision was made by the Benlysta Safety Review Team (SRT) in April 2020 to stop manual categorization (using the PSAP adjudication categories described in Appendix 6 of the Week 52 double-blind treatment period RAP) of Year 2-5 deaths and malignancies for Year 3 reporting onwards for the following reasons:

- Many events cannot be definitively categorised using the limited information available from verbatim primary cause of death/malignancy diagnosis. Clinical corroboration of the reported terms is generally not possible. Ambiguities often cannot easily be resolved because it is not possible to query the site staff to follow up with the subject and/or review medical records (as was done during the treatment period of the study).
- As a result, it is particularly difficult to overcome the inherent difficulties introduced by manual categorisation, such as inconsistencies between reviewers/review sessions and the need to protect against the potential for hidden biases/subjective interpretation of extremely minimal information.
- Therefore manual categorisation adds little value above programmatic coding.

Therefore summaries of deaths and malignancies by manual categorisation to GSK PSAP category have been omitted from this RAP Amendment Version 1 and the mock shells.

5.6.1. Handling of Missing Data

All safety summaries will use the observed data, which are the data collected or observed for the subject with no imputation for missing data, unless otherwise stated.

5.6.1.1. Handling of Missing and Partial Dates

Element	Reporting Detail
General	
 Partial dates will be displayed as captured in subject listings.
Date of Birth	
 Only year of birth is collected on the CRF. Day will be set to 30 and month will be set to JUNE for all subjects.
Date of SLE diagnosis	
 For records where month and day are missing for diagnosis date, impute with 01 for day and January for month to assume that the duration was the longest possible duration. For records where the day only is missing for start date, impute with 01 for day to assume that the duration was the longest possible duration.
Date of Death	
 For records where month and day are missing for date of death, impute 01 for day and January for month. For records where the day only is missing, impute 01 for day. Unless there is other information available which indicates a subject was alive at a later date, in which case the last known alive date will be imputed as the date of death i.e. maximum (imputed date of death, latest last known alive date). This will only be done where a partial date of death is recorded.
Last known to be alive date	
 For records where month and day are missing for last known to be alive date, impute 01 for day and January for month. For records where the day only is missing, impute 01 for day. For subjects with a survival status of withdrew consent reported on the eCRF at a follow-up visit, there is no date of last known alive collected. In these cases, the date of follow-up contact will be used as the date the subject was last known alive.
Date of diagnosis (new malignancies)	
 For records where month and day are missing for date of diagnosis, impute 01 for day and January for month. For records where the day only is missing, impute 01 for day.

5.6.2. Derived and Transformed Data**5.6.2.1. Race Hierarchy Rule**

If multiple race categories are checked on the eCRF, the subject will be assigned to a unique race group based on which of the races checked appears first in the list below:

- Native Hawaiian or Other Pacific Islander
- American Indian or Alaska Native

- Asian
- Black or African American
- White

For example, if Black or African American and Asian are both checked, then the subject will be assigned as Asian since it appears highest in the list. In the race and racial combination details table, subjects with multiple race categories checked will be reported in the race per the hierarchical rule as well as in the multiracial category. Subjects who select more than one Asian category and no other non-Asian categories will be represented in the Mixed Asian Race category as well as the Asian category. Similarly, subjects who select both white categories and no non-white categories will be represented in the Mixed White Race category as well as the White/Caucasian category. The Mixed Asian Race and Mixed White Race categories will only appear in the table if a subject selects multiple Asian or multiple white categories, respectively.

For the race categorization of Black vs Other, if a subject selects multiple races they will be assigned “Black” if any of the races is “Black or African American”, i.e., the hierarchical rule will not apply in this instance (see Section 5.2).

5.6.2.2. Study Day

Study Day is the number of days from the treatment start date to a study date of interest (e.g. event start date) and is calculated as follows:

If condition is...	Then Study Day is...
study date < treatment start date	study date – treatment start date
study date is ≥ treatment start date	study date – treatment start date + 1

Note: Study Day cannot be zero. If either date is missing, then Study Day is missing.

Note: Study day is calculated from treatment start date in the Week 52 double-blind treatment period part of the study.

5.6.2.3. Year Intervals

All-cause mortality and malignancies (including NMSC) will be summarized by follow-up year. The nominal visit will be used for yearly summaries. There will be no slotting of visits into years using dates.

The planned study day of each year is as follows (using a 365-day calendar year):

Study Year	Planned Study Day of Visit
Week 52	Day 365 ± 7
Year 2 Follow-Up	Day 730 ± 30
Year 3 Follow-Up	Day 1095 ± 30
Year 4 Follow-Up	Day 1460 ± 30
Year 5 Follow-Up	Day 1825 ± 30

Note: Treatment start date is Day 1.

Note: The protocol study calendar refers to Week 52 as Day 364 (and uses Day 0 terminology). This equates to study Day 365, as calculation of study day does not allow a Day 0 but starts at Day 1.

5.6.2.4. Deaths

Deaths will be identified using data reported on the survival status form of the eCRF (i.e. survival status = DEAD).

In addition, sites have been instructed to collect additional data on deaths due to the COVID-19 pandemic. If COVID-19 was the primary reason for death, then the “Primary cause of death” field on the survival status form in the eCRF was to be recorded using specific COVID-19 terms. In the reporting, COVID-19 deaths will be identified per custom MedDRA query (CMQ), using GSK TOI LISTID 318947.

For deaths where COVID-19 may have been a contributory factor but was not the primary cause of death, sites have been instructed to add a comment in the eCRF. These comments are not included in the database, but will be extracted directly from the EDC (INFORM) system, for inclusion in the Year 3, 4 and 5 follow-up reports.

Deaths will be assigned to Week 52, Year 2 follow-up, Year 3 follow-up, Year 4 follow-up or Year 5 follow-up based on the nominal visit of the survival status form where death is reported. For deaths reported during the Week 52 double-blind treatment period, this is equivalent to deaths which occurred during the on-study period (see Section 9.1.1 of the separate Week 52 double-blind treatment period RAP) i.e. deaths reported up to study Day 372.

Date of death is not collected on the Week 52 survival status form. In these cases the date of death will be derived as the end date of the SAE with fatal outcome. For deaths reported after Week 52, date of death is collected on the survival status form.

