7.2.2 Serious Adverse Events

Serious Adverse Events (SAEs) that occur from the start of study agent at Day 0 through Week 52 and regardless if study agent is discontinued early must be recorded on the SAE eCRF within 24 hours of site personnel becoming aware of a SAE, regardless of expectedness. All fields of the SAE eCRF should be completed, but completion of the report should not be held until all information is available. Follow-up information and corrections should be added to the SAE eCRF within 24 hours of site personnel becoming aware of the follow-up information as described in the ePharmaSolutions document portal.

SAEs that occur after Week 52 (or 4 weeks after the last dose of IP if a subject has withdrawn consent to participate in the first year monthly study visits) and that are assessed by the investigator as possibly related to study agent taken the first year must be reported to the Sponsor as outlined in the ePharmaSolutions document portal.

Prior to study drug administration, any SAE assessed as related to study participation (e.g., protocol mandated procedures, invasive tests) will be recorded on the SAE worksheet and reported as described above from the time a subject consents to participate in the study. Pre-treatment SAEs will not be documented on the SAE eCRF.

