2.3. Study Design

This is a global, multi-center, randomized, double-blind, placebo-controlled, 52-week study to assess mortality and AESI in adults with active, autoantibody-positive SLE treated with belimumab plus standard therapy vs placebo plus standard therapy. It was planned that approximately 4,000 subjects would be randomized (1:1) to belimumab plus standard therapy or placebo plus standard therapy. Randomization was stratified for region (US/Canada vs Central America/South America/Mexico vs Europe/Australia/Israel vs Asia; see [Appendix 1: Countries by Region: Countries by Region](#) for details of countries and regions), Safety of Estrogen in Lupus National Assessment Systemic Lupus Erythematosus Disease Activity Index (SELENA SLEDAI) score (≤ 9 vs ≥ 10), and steroid dose (≤ 7.5 mg/day vs > 7.5 mg/day prednisone or equivalent). There was no minimum score required for the SELENA SLEDAI to be eligible for this study.

Subjects were to receive investigational product (IP) on Days 0, 14, 28, and every 28 days thereafter through Week 48 with a final visit conducted at Week 52. Following the 52-week study, all subjects were to be contacted annually through Year 5 to assess mortality and malignancy (including NMSC). Subjects who discontinued treatment at any time during the study but did not withdraw consent were to be followed at 28-day intervals through Week 52. If the subject withdrew consent prior to Week 52, an attempt was to be made to assess mortality and occurrence of malignancy (including NMSC) at Week 52 and annually for Years 2 to 5. See protocol Section 3.1 for further details. Protocol time windows are ± 30 days for annual follow-up contacts from Year 2 to Year 5.

In the Years 2 to 5 post-treatment follow-up period, subjects no longer receive study treatment, but instead receive physician directed standard of care.

Data collection in the Years 2 to 5 post-treatment follow-up period was limited and included information on survival status, information on new primary malignancies (including NMSC) and start date of first exposure to commercial Benlysta (other than investigational product during Year 1). For Years 2 to 5, annual follow-up was planned to be conducted via telephone.

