7. SAFETY ANALYSES

The safety summaries will be based on the As-Treated population, unless otherwise specified. Summaries will be presented by treatment group and overall.

Only serious adverse events (SAEs) and adverse events of special interest (AESI) were collected during the Week 52 double-blind treatment period of the study. Serious adverse events and AESIs were not collected as part of the clinical database for the Years 2 to 5 post-treatment follow-up period, therefore no summaries of adverse event data will be produced.

Any serious adverse events reported via paper CRFs during the Years 2 to 5 post-treatment follow-up period will be reported from the GSK safety database as part of the Clinical Study Report (CSR), but no summaries or listings will be produced by the programming group (as this data does not form part of the clinical database).

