3. STUDY DESIGN

This is a global, multi-center, randomized, double-blind, placebo-controlled, 52-week study to assess mortality and AESI in adults with active, autoantibody-positive SLE treated with belimumab plus standard therapy vs placebo plus standard therapy. Approximately 4,000 subjects will be randomized (1:1) to belimumab plus standard therapy or placebo plus standard therapy. Randomization will be stratified for region (US/Canada vs Central America/South America/Mexico vs Europe/Australia/Israel vs Asia; see [Appendix 1: Countries by Region](#) for details of countries and regions), Safety of Estrogen in Lupus National Assessment Systemic Lupus Erythematosus Disease Activity Index (SELENA SLEDAI) score (≤ 9 vs ≥ 10), and steroid dose (≤ 7.5 mg/day vs >7.5 mg/day prednisone or equivalent). There is no minimum score required for the SELENA SLEDAI to be eligible for this study.

Subjects will receive investigational product (IP) on Days 0, 14, 28, and every 28 days thereafter through Week 48 with a final in clinic visit conducted at Week 52. Subjects who discontinue treatment at any time during the study but do not withdraw from study visits will be followed at 28-day intervals through Week 52. If the subject withdraws from study visits prior to Week 52, an attempt will be made to assess mortality and occurrence of malignancy (including NMSC) at Week 52 and annually for Years 2 through 5. See protocol Section 3.1 for further details. If a subject is not contactable (withdrew consent or lost to follow-up), where allowed by individual subject's legal consent status and individual country regulations, sites may utilize other available records to perform a mortality assessment at Week 52 - this may include search of public records aided by an independent party.

An Independent Data Monitoring Committee (IDMC) will review unblinded safety data until the data are locked and analyzed. The IDMC will monitor all SAEs (including all-cause mortality), serious infections, opportunistic infections and other infections of interest, malignancies (including NMSC), selected serious psychiatric events, suicidality and serious infusion and hypersensitivity reactions. Details of the summaries provided to the IDMC by an Independent Statistical Data Analysis Center (SDAC) are described in the IDMC Charter and IDMC Report Template.

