9.5.12. Mortality and Protocol-Defined AESI

Mortality status will be derived from the SAE data, where outcome is fatal.

The derivation for the protocol-defined AESIs are provided in the table below. Treatment emergent AESIs (see Section 9.5.13 and Section 9.5.15) only will be summarized.

Where the protocol defined AESI utilize definitions from the PSAP, the detailed derivations from the PSAP are provided in [Appendix 6: PSAP Sections for AESI Reporting](#). AESI are identified per the preferred terms and other criteria described in the PSAP.

Protocol-Defined AESI (see Section 2.2.1 and Section 2.2.3 for clarification)	Definition	Programming Derivation (Protocol Definition)
Serious infections	SAEs within Infections and Infestations SOC.	SOC=Infections and Infestations & AESER = 'Y'
Opportunistic infections and other infections of interest	"All Infections" per PSAP definition to cover all OI and infections of interest.	CQ06NAM ne " or CQ07NAM ne " or CQ08NAM ne "
Non-melanoma skin cancers (NMSC)	NMSC per PSAP definition.	CQ00MLFL = 'Y' and CQ03NAM ne " and CQ03NMFL = 'Y'
Malignancies (excluding NMSC)	PSAP defined, "all malignancies excluding NMSC".	[CQ00MLFL = 'Y' and (CQ01NAM ne " or CQ02NAM ne " or (CQ03NAM ne " and CQ03NMFL ne 'Y'))] Or (CQ04NAM ne " and CQ04NPFL = 'Y')
Psychiatric events suggesting serious mood disorders and anxiety	Serious events from the depression CMQ (PSAP defined – depression including mood disorders and anxiety).	CQ09NAM ne " and AESER = "Y"
Suicidality (C-SSRS)	Any treatment-emergent C-SSRS suicidal ideation (1-5) or suicidal behavior (6-10) (defined in Section 9.5.15) – i.e. maximum ideation score worsens relative to pre-treatment or maximum behavior score worsens relative to pre-treatment	C-SSRS Ideation categories 1-5 and Behavior categories 6-10; any subject with ideation or behavior that is treatment-emergent (defined in Section 9.5.15).
Serious infusion and hypersensitivity reactions	Serious infusion and hypersensitivity reactions per the PSAP definition. Includes all SAEs from the anaphylactic reactions CMQ broad search (see Section 11.2.4, includes events on the day of the infusion or within 3 days after the infusion).	CQ05NAM ne " and AESER='Y' and AEINF3FL='Y'

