All fatalities that are reported while a subject is eligible for SAE reporting will be identified in the clinical database and subsequently adjudicated by the GSK SRT into a general category of death ([Section 16.5](#)).

Post-study fatalities that are captured in ARGUS prior to CSR approval, but are not captured in the clinical database, will be described within the CSR text but cannot be included in statistical post-text displays. Post-study fatalities are not adjudicated by the SRT.

Additionally, for the BEL115467 “BASE” study, any fatalities that are reported annually (in the Year 2-5 post-treatment follow-up) via survival status updates in the CRF and not captured in ARGUS, will not be adjudicated by the SRT.

Section 16: GSK SRT Adjudication of Adverse Events of Special Interest

Adverse events of special interest (AESI) are identified per the preferred terms ([Section 17.1](#)) and other criteria described in [Section 15](#). The following AESI are adjudicated in-stream at the subject level by GSK during regular SRT meetings or during quarterly adjudication, and then prior to database release for CSR reporting purposes, per the criteria described below.

In-stream review/adjudication of AESI is conducted as follows:

- Review/Adjudication of AESI in ARGUS

Safety Evaluation and Risk Management (SERM) lists all events in ARGUS each month for SRT to review. AESIs are adjudicated at SRT meetings and entered onto Excel spreadsheets maintained by SERM. These spreadsheets are cumulative and contain events for all belimumab studies (clinical trials, post-marketing studies and spontaneous reports). SERM refer to these as “Cumulative AESI spreadsheets”. SERM use these spreadsheets to tabulate the numerators used for PBRER/DSUR rates (see PSAP Section 7.6). The numerators are typically updated shortly after the Data Lock Point, and updated numerators are then used for PBRER/DSUR updates. The numerators are tracked in spreadsheets referred to as “AESI numerator spreadsheets”.

- Review/Adjudication of AESI in the Clinical Database

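### Years 2 to 5 mortality tables take deaths only from the eCRF survival form, with no reconciliation against the sponsor's safety database, so a death the sponsor knows of can be missing from the all-cause counts and rates

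*SAP*

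**What the plan says.** The SAP file holds two plans, one for the 52-week treatment period and one for Years 2 to 5. The Years 2 to 5 endpoint is all-cause mortality (Section 2.2).

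- **Source of deaths, Years 2 to 5 (Section 5.6.2.4):** "Deaths will be identified using data reported on the survival status form of the eCRF (i.e. survival status = DEAD".
- **SAEs in Years 2 to 5 (Section 7):** they are not collected in the clinical database. Those that arrive on paper are reported in the clinical study report from the safety database, but "no summaries or listings will be produced by the programming group (as this data does not form part of the clinical database".
- **Fatalities held only in the safety database (Week 52 plan, Appendix 6, PSAP Section 15.5):** post-study deaths captured there and not in the clinical database "will be described within the CSR text but cannot be included in statistical post-text displays". This is programme-wide text. The Years 2 to 5 plan uses the current PSAP (Sections 1 and 5.6).
- **What must still be reported (Protocol 7.2.2):** SAEs after Week 52 that are "assessed by the investigator as possibly related to study agent taken the first year must be reported to the Sponsor". For subjects who withdrew consent to the monthly visits, this starts 4 weeks after the last dose.
- **Source of deaths to Week 52 (Week 52 plan, Section 9.5.12):** "Mortality status will be derived from the SAE data, where outcome is fatal".

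**The concern.** An all-cause mortality table should contain every death the sponsor knows of. Here two channels can carry a death after Week 52, only one reaches the tables, and no step checks that they agree. The channel left out carries the deaths that matter most in a safety trial: those an investigator thinks study agent may have caused. It also covers subjects who left the monthly visits and may have no annual form.

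The source of deaths changes at Week 52 as well, from fatal SAEs to the survival form, while the cumulative mortality tables run from treatment start across that change. At stake are the completeness of rates reported to health authorities and the comparison between arms if omissions are uneven.

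**Working it through.** **1. Is there a reconciliation step?**

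- For Week 52 deaths, Section 5.6.2.4 states that the survival form and the on-study deaths are equivalent, and takes the date of death from the fatal SAE. The two sources are tied together.
- For later years no such statement appears. Date and cause of death both come from the form.
- PSAP Section 16 (Appendix 6 of the Week 52 plan) describes checking serious events of special interest between the safety database and the clinical database. It works on adverse event data, which the clinical database does not collect in Years 2 to 5, and it is not written for that period.
- The study-specific paragraph in PSAP Section 15.5 covers the reverse mismatch: deaths on the form but not in the safety database, which are not adjudicated.

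So the plan foresees that the sources can differ and gives no rule for a death that is only in the safety database.

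**2. What happens to such a subject under Section 5.6.2.6?** No event is counted. Person-time ends at the latest last known alive date. For a subject who never entered follow-up it is capped at 365 days.

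**3. The plan's own figure.** The only stated precision is ±0.46% for the first-year mortality difference (Protocol 8.4 and 8.4.1; Week 52 plan 5.1). Half-width = 1.96 × √(2p(1−p)/n):

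- n = 2,500 per arm, p = 0.0068: 0.456%
- n = 2,000 per arm, p = 0.00564: 0.464%

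Both round to 0.46%, so it reproduces. It concerns Week 52; the documents give no precision figure for Years 2 to 5.

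**4. Size of one omitted death.** The planned rate (Section 5.6.2.7) is 100 × subjects with an event / subject-years, cumulative from treatment start. Inputs: 2,000 per arm, and mortality of 0.504% (6/1,190) to 0.564% (14/2,484). Assumptions: these apply as constant yearly rates, and follow-up is complete.

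- Subject-years by Year 5: 2,000 × 5 = about 10,000 per arm.
- Expected deaths: 10,000 × 0.00504 = 50.4, to 10,000 × 0.00564 = 56.4.
- One omitted death: 100 × 1/10,000 = 0.01 per 100 subject-years, or 1/56.4 = 1.8% to 1/50.4 = 2.0% of the arm's deaths.
- Three omitted in one arm only: 0.03 per 100 subject-years.

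**5. The same with loss to follow-up.** Assumptions: 0.564 per 100 subject-years, Year 1 complete, then constant yearly loss. Half-width of the rate difference = 100 × 1.96 × √(2d)/T, with d deaths and T subject-years per arm. Section 7.1 specifies no interval for these rates; the half-width serves only as a scale.

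| Loss per year | Subject-years per arm | Deaths per arm | Shift, 1 omitted | Shift, 3 omitted | 95% half-width |
|---|---|---|---|---|---|
| 2% | 9,552 | 53.9 | 0.010 | 0.031 | 0.213 |
| 5% | 9,109 | 51.4 | 0.011 | 0.033 | 0.218 |
| 10% | 8,418 | 47.5 | 0.012 | 0.036 | 0.227 |

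Three omissions in one arm move the difference by about a seventh to a sixth of that half-width.

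**The case against.** Nothing stops a site from entering a death on the survival form from any source, and a site that reports a fatal related SAE knows of the death. Data are cleaned continuously, and late entry is expected (Sections 2.4 to 3.2 and the COVID-19 text in 2.3). The deaths in question are not hidden, because Section 7 sends safety-database SAEs into the study report. The PSAP sentence on fatalities is general, and its reach to Years 2 to 5 is not explicit. There is no hypothesis test and no study treatment in this period.

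All of this stands. It makes omission possible rather than shown, and probably rare. It does not supply the missing check.

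Three stronger readings are tempting and are not supported:

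- **That such subjects are carried as alive.** Person-time stops at the last known alive date, and Section 7.1 shows lost to follow-up, withdrew consent and not completed apart from alive. The defect is a lost event.
- **That five-year mortality is biased low because the Week 52 records search is not repeated.** At Week 52, "sites may utilize other available records to perform a mortality assessment at Week 52 - this may include search of public records"; later, "For Years 2 to 5, annual follow-up was planned to be conducted via telephone". That search was permissive, and silence in the later plan does not forbid it. The bias is also conditional. Suppose a fraction L is lost evenly over Years 2 to 5 and the death hazard after loss is k times that of those followed. Then true/observed rate = 1 + 0.4 × L × (k−1), since 2L of 5 years per subject go unobserved. L = 0.1, k = 1.5 gives 2% understatement; L = 0.2, k = 2 gives 7%; L = 0.3, k = 3 gives 19%; k = 1 gives none. The documents give neither L nor k.
- **That safety-database deaths belong directly in the main tables.** After Week 52 only possibly related SAEs must be reported, so this source finds deaths selectively. A subject capped at 365 days would regain later time only by dying, while comparable survivors stay capped. Relatedness could also be judged after the January 2019 unblinding.

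**Conclusion.** The point holds in a limited form. By stated rule, the Years 2 to 5 mortality tables use the survival form alone, safety-database SAEs reach no table or listing, and no step reconciles the two. A death known to the sponsor can be missing from the all-cause counts and rates while described in the report text.

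The number affected cannot be established from the documents. Each omission is worth about 0.01 per 100 subject-years in an arm, against an expected rate of 0.504 to 0.564. This rests on 2,000 subjects per arm, the planning mortality applied as a constant yearly rate, and near-complete follow-up. The effect on the overall rate is small. The reason to act is that the deaths most exposed are those judged possibly related, and the check is cheap.

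**What to change.** In Section 5.6.2.4 of the Years 2 to 5 plan:

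1. Before each annual data cut and before the Year 5 database freeze, match fatal cases for trial subjects in the safety database to the survival form, by subject. Produce one reconciliation listing.
2. For each unmatched case, query the site to complete the survival form where consent allows. Mark in the listing which forms were completed after such a query.
3. Keep Tables 3.1 to 3.8 on the survival form. Add one sensitivity version of Table 3.6 that counts all known deaths with a source flag and ends person-time at the date of death. A footnote should say that safety-database reporting after Week 52 is limited to possibly related events, so this source is outcome-dependent.

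The cost is some plan wording, one listing and one extra table per reporting effort, and rates that may be slightly less favourable. The same section already draws COVID-19 comments from outside the analysis database for the reports, so bringing in outside information has a precedent. A repeat public-records search is not part of this request.
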